3.4 IdeS Clinical Studies

A phase I study first in man single ascending dose study in 29 healthy subjects showed that IdeS was safe and well tolerated in doses up to 0.24 mg/kg body weight (BW). The study demonstrated that IdeS could be administered at 0.24 mg/kg BW with a favourable safety profile. It also showed that IdeS could effectively reduce the levels of plasma IgG and that newly synthesised IgG was not detectable until two weeks after dosing. At the two highest

doses, 0.12 and 0.24 mg/kg BW, IdeS completely cleaved the pool of plasma IgG within 14 minutes after initiation of infusion and the level of intact IgG was reduced to less than 5% of its original level. In addition, newly synthesized IgG was not detectable until two weeks after dosing (HMed Doc. No. 2014-003). The data clearly indicates that a single dose of IdeS is superior to both plasmapheresis and immunoadsorption with respect to efficiency and rate of plasma IgG reduction. Since IdeS degrades IgG there was concern that study subjects would have an increased risk of infection and that subclinical infections (e.g., pneumococci) would pose a problem. Therefore, subjects received antibiotic prophylaxis until plasma IgG levels had returned to levels ≥ 4.5 g/L and there were no signs of an increased rate of infections within the study group. The adverse events that were reported, none of which were reported as serious, were as anticipated from the biological nature of the drug. Hence, headache and fatigue were more common in the IdeS treated subjects compared to placebo. One possible infusion reaction was reported among the placebo treated subjects and one among the IdeS treated, the latter resolved within 60 minutes after treatment with antihistamine and glucocorticoids and the infusion was completed. All adverse events were mild or moderate.

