One phase II study was completed at Uppsala University Hospital, Sweden in March 2015. The study was a single arm study with ascending doses of IdeS in 8 chronic kidney disease (CKD) patients on the kidney transplantation waiting list and sensitized to human leucocyte antigens (HLAs). The patients enrolled were diagnosed with CKD, in dialysis and on the waiting list for a kidney transplant. However, transplantation was not part of the study protocol. The study showed that one or two doses of IdeS at 0.25 mg/kg BW in the majority of the patients resulted in HLA antibody levels, acceptable for transplantation within 24 hours from dosing. In addition, in all patients having a significant pre-dose panel-reactivity the percentage panel reactive antibody (PRA) was reduced one hour after IdeS treatment. It was also concluded that in the majority of patients the complement dependent cytotoxic crossmatches were converted to negative already one hour after a single dose of IdeS (0.12 or 0.25 mg/kg BW) and the crossmatches remained negative for one week. There were a total of five SAEs reported in the study of which four were classified as probable or possible related to study drug, i.e., suspected serious adverse reactions (SARs). Three of the SARs were infections and one myalgia. Two phase II studies using IdeS in sensitized patients prior to kidney transplantation are currently ongoing in Uppsala, Sweden and Los Angeles, US.

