3.7 Risk/Benefit and Ethical Assessment

A starting dose of 0.25 mg/kg BW has been selected for this study. The phase I study did not identify any dose limiting factors even at the highest tested dose (0.24 mg/kg BW) and CKD patients in a completed phase II study in Sweden were exposed to a total dose of 0.5 mg/kg BW with acceptable safety profile. In addition, the doses of 0.25 mg/kg and 0.5 mg/kg BW are well covered by the no observed adverse effect level (NOAEL) of 2.0 mg/kg BW obtained in toxicology studies. The pharmacokinetics (PK) of IdeS in asymptomatic TTP patients is expected to be similar to what is observed in healthy subjects, thus, a starting dose of 0.25 mg/kg BW is considered to be safe.

Since IdeS effectively removes the IgG pool, there may be an increased risk of infection. In order to minimise the risk for bacterial infections all patients treated with IdeS will receive a two-week regimen of prophylactic antibiotics following IdeS dosing. Patients will be screened for viruses (Hepatitis B, C and human immunodeficiency virus [HIV]) and on-going infections and patients having clinical signs of on-going infections will be excluded from the study. Patients will be instructed to contact the principal investigator immediately if they have any sign of infection. In case of infection in a patient with low IgG plasma levels, intravenous immunoglobulin may be indicated.

It has been demonstrated in laboratory studies that IdeS cleaves biologics based on human IgG including; IVIg, basiliximab, rituximab, adalimumab, denosumab, belatacept and etanercept. IdeS also cleaves rabbit anti-thymocyte globulin (rATG) but not equine anti-thymocyte globulin (ATGAM). The optimal interval between HMedIdeS administration and these biologics have not been defined (HMed Doc. No. 2012-003). Rituximab is cleaved by IdeS and therefore rituximab treatment within 7 days prior to IdeS dosing will not be allowed in TTP patients. The concomitant use of these other biologics and IdeS will continue to be closely monitored in order to mitigate any changes in the efficacy of these biologics.

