Patients found eligible at the screening visit will be included in the study. At visit 2 an eligibility check will be performed pre-dose within 60 min prior to IdeS infusion (inclusion/exclusion criteria, medical history, concomitant medication, vital signs, body temperature, urinalysis, blood sampling for pregnancy test, safety laboratory parameters (including [REDACTED], [REDACTED] and immunoglobulins (IgG, IgM and IgA), ADAMTS13 activity, ADAMTS13 antibodies, [REDACTED], IdeS concentration, total IgG and F(ab')₂ fragment concentrations (PD) and ADA. Hydrocortison, paracetamol and antihistamine (chlorphenamine maleate) will be administered pre-dose to prevent/minimise risk of infusion reactions. Weight will be measured and prophylactic antibiotics will be administered.

Patients will receive a single intravenous dose of IdeS over 30 minutes.

At 2, 6 and 24 h post IdeS infusion blood sampling for determination of total IgG and F(ab')₂ fragment concentrations (PD), ADAMTS13 activity and antibodies, safety laboratory parameters, body temperature and [REDACTED] as well as urine sampling will be performed. Assessment of vital signs and ECG will be performed at 6 hours post dosing.

At 45 min, 2, 6 and 24 h post IdeS infusion sampling for determination of IdeS concentration will be performed.

AEs and concomitant medication will be recorded on the applicable CRFs throughout the visit.

Visit 3, 4, 5 and 6 (Days 3, 7, 10 and 14 respectively)

At visits 3, 4, 5 and 6 safety laboratory parameters, IdeS concentration, total IgG and F(ab')₂ fragment concentrations (PD), AEs and concomitant medication will be assessed as well as vital signs, ADAMTS13 activity, ADAMTS13 antibodies and [REDACTED]. Urine will be collected for urinalysis. Additionally, at visits 3, 4 and 6 ADA will be measured. Body temperature, weight and 12-lead resting ECG will only be measured at visit 6.

Visit 7 (Day 30)

At visits 7 safety laboratory parameters, total IgG and F(ab')₂ fragment concentrations (PD), AEs and concomitant medication will be assessed as well as vital signs, weight, body temperature, 12-lead resting ECG, ADAMTS13 activity, ADAMTS13 antibodies and [REDACTED]. A physical examination will be performed. Urine will be collected for urinalysis.

Visit 8 (End of Study, Day 64)

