7.3 Study Flow Chart

Table 2. Study flow chart

Visit number	1	2	3	4	5	6	7	8
	Screening	Treatment period						EOS
Assessment/Day	-28 to -4	0-1	3	7	10	14	30	64
Informed Consent	x							
Demographics	x							
Medical history	x	x ^b						
Inclusion/exclusion	x	x ^b						
Physical examination	x						x	x
Weight	x	x ^b				x	x	x
Height	x							
Vital signs (blood pressure & pulse respiratory frequency)	x	x ^a	x	x	x	x	x	x
Body temperature	x	x ^c				x	x	x
Clinical chemistry (incl. immunoglobulins and ██████████), haematology ██████████, ██████████ urinalysis	x	x ^c	x	x	x	x	x	x
Serum pregnancy test	x	x ^b						x
ADAMTS13 activity	x	x ^c	x	x	x	x	x	x
ADAMTS13 antibodies	x	x ^c	x	x	x	x	x	x
Adverse events	x	x	x	x	x	x	x	x
12-lead ECG	x	x ^a				x	x	x
IdeS infusion		x						
Hydrocortison, paracetamol, antihistamine		x ^b						
Prophylactic antibiotic		x						
IdeS concentration (PK) ██████████		x ^d	x	x	x	x		
██████████		x ^c	x	x	x	x	x	x
PD sampling (IgG SDS-PAGE, IgG and F(ab') ₂ concentration)		x ^c	x	x	x	x	x	x
ImmunoCAP IgG (ADA)		x ^b	x	x		x		x
ImmunoCAP IgE	x							
HIV, Hepatitis B and C	x							
Concomitant medication	x	x	x	x	x	x	x	x

^apredose and 6 h post dose

^bpredose

^cpredose, 2 h, 6 h and 24 h post dose

^dpredose, 45 min (+/- 5 min), 2 h (+/- 15 min), 6 h (+/- 30 min) and 24 h (+/- 2 h) post dose

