8.2.4 Body Temperature

Body temperature will be measured at screening and study visit 2. At visit 2/dosing, body temperature will be recorded pre-dose, 2, 6 and 24 hours post-dose as well as on days 14, 30 and 64.

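### No body temperature is scheduled between 24 hours and day 14, although patients attend on days 3, 7 and 10, inside the expected period of IgG depletion

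*Protocol*

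**What the plan says.** Three places in the protocol set the temperature schedule, and they agree.

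- Section 7.2, on visits 3 to 6 (days 3, 7, 10 and 14): "Body temperature, weight and 12-lead resting ECG will only be measured at visit 6".
- Section 8.2.4, on the dosing visit and after: "body temperature will be recorded pre-dose, 2, 6 and 24 hours post-dose as well as on days 14, 30 and 64".
- Table 2 (section 7.3): the temperature row is marked at screening, visit 2 and visits 6, 7 and 8, and is blank at visits 3, 4 and 5.

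Temperature is not included under vital signs. Table 2 labels that row "Vital signs (blood pressure & pulse respiratory frequency" and gives temperature a row of its own. Section 8.1.3 likewise describes only blood pressure, pulse and respiratory frequency.

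On the background risk, section 3.4 reports that in phase I, at 0.12 and 0.24 mg/kg, "the level of intact IgG was reduced to less than 5% of its original level", and that "newly synthesised IgG was not detectable until two weeks after dosing". Section 3.7 draws the consequence: "Since IdeS effectively removes the IgG pool, there may be an increased risk of infection". On the four suspected serious reactions in the completed phase II study of eight patients with chronic kidney disease, section 3.4 says: "Three of the SARs were infections and one myalgia".

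**The concern.** Temperature is a basic objective sign of infection. The schedule takes it around the infusion and again on day 14, when the depletion period is expected to be ending, but not on the visits in between. Patients are already at the clinic on those days and other vital signs are being recorded.

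Safety is the primary objective, and section 14.2.3 includes body temperature among the safety data to be tabulated. With six patients planned, each patient's safety record carries a lot of weight. If a patient became febrile on day 7 without symptoms worth reporting, the planned data would contain no temperature to show it. If a patient stayed afebrile, the planned data could not show that either. No physical examination is scheduled between screening and day 30, so a routine examination would not prompt a reading.

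**Working it through.** The plan states no figure to reproduce, and the sample size has no formal basis. The check compares the schedule with the depletion period.

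**Inputs**

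- Post-dose temperature times (7.2, Table 2, 8.2.4): 2 h, 6 h, 24 h, days 14, 30 and 64. That is 6 readings.
- Attended visits between the 24-hour reading (day 1) and day 14 (Table 2): days 3, 7 and 10.
- First detection of new IgG in phase I (3.4): two weeks, about day 14.

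**Step 1: length of the gap.** Day 14 − day 1 = 13 days with no scheduled temperature.

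**Step 2: visits inside the gap.** Days 3, 7 and 10 make 3 visits. Of the 4 visits covered by the sentence in 7.2, 3 have no temperature.

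**Step 3: position relative to depletion.** Days 3, 7 and 10 are all earlier than day 14, so all 3 fall before new IgG was detectable in phase I. The 2 h, 6 h and 24 h readings also fall in this period, because phase I showed IgG cleaved within 14 minutes of the start of infusion. The depletion period therefore has some temperature data, but only on its first day and at its end.

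**Step 4: what is collected on days 3, 7 and 10 (7.2, Tables 2 and 3).**

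| Collected | Not collected |
|---|---|
| Blood pressure, pulse, respiratory frequency | Body temperature |
| CRP, white cell count with differential, immunoglobulins | Weight |
| Urinalysis including nitrite | ECG |
| ADAMTS13 activity and antibodies, LDH, haptoglobin, reticulocytes | Physical examination |
| Adverse events, concomitant medication | |

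**Step 5: effect of adding temperature at the three visits.**

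- Post-dose readings per patient: 6 + 3 = 9.
- Gaps from day 1 to day 14: 3 − 1 = 2, 7 − 3 = 4, 10 − 7 = 3, 14 − 10 = 4. The longest falls from 13 days to 4.

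**Step 6: link to dose escalation.** Section 5.3 has safety data to day 14 evaluated before escalation. Section 5.1 names clinical chemistry, haematology, coagulation and adverse events as the content, and 5.3 points to Table 3. Table 3 does not list temperature. A fever recorded as an adverse event would reach the review, but a temperature reading is not in the listed package on any day. Adding temperature to the visit schedule would not change that by itself.

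**The case against.** The strongest reply is that this is a deliberate and consistent choice and that the days in question are well covered. Much of that stands.

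- *Consistency.* The three descriptions do not conflict, so this is a design choice to improve and not a contradiction.
- *Other surveillance.* A reader might infer that infection on days 3 to 10 would be found only through patient report and CRP. The documents do not support that. The white cell differential, urinalysis, pulse, blood pressure and respiratory frequency are all scheduled. Adverse events are collected by open question and by observation (8.4.5). Patients are told to report any sign of infection at once (3.7), and nothing bars an unscheduled temperature.
- *Prophylaxis.* All patients receive antibiotics for two weeks (8.3.2). Phase I, which supplies the IgG figures, saw no sign of more infections under prophylaxis. The phase II infections arose in dialysis patients, a different population.
- *TTP relapse.* Section 3.1 lists fever as a possible feature of acquired TTP, so a reader might infer that relapse would be missed. It would not rest on temperature: ADAMTS13 activity and antibodies and the haemolysis markers are measured at each of these visits.
- *Premedication.* A reader might infer that the early readings are a poor measure of fever because of premedication, or that all lie within 24 hours of it. The documents give no duration of antipyretic effect. Premedication is given before dosing and sampling times run from the start of infusion (7.2), so the nominal 24-hour reading falls more than 24 hours after premedication.
- *Endpoint status.* Temperature sits under other assessments (8.2), and the primary endpoint in 4.2.1 does not name it. The link is through 14.2.3.
- *Residual gaps.* Three spot readings still leave intervals of up to 4 days, so intermittent fever would still depend on patient report.

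These points reduce the size of the problem. They do not supply a scheduled temperature in the 13-day gap, and none is a reason to leave out a reading when the patient is present and other vital signs are being taken. Laboratory cover also has a limit as a safety record. Section 8.1.5.1 has clinically significant abnormal laboratory findings reported as adverse events, while 8.4.6 restricts this to findings that are serious or lead to discontinuation. How an isolated CRP rise would be recorded is therefore unclear.

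**Conclusion.** The point holds as a modest gap in objective safety data. No temperature is scheduled for 13 days after the 24-hour reading, and three attended visits in that interval record other vital signs without it.

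The conclusion that those visits fall in the depletion period assumes that the phase I time course in healthy subjects applies here. The protocol expects similar pharmacokinetics in these patients (3.6, 3.7) but gives no IgG time course for them. The conclusion concerns scheduled readings only. It does not mean that fever, infection or relapse would go undetected.

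A reader might also infer that the day-14 escalation decision lost data it was meant to use. The documents do not show this, because temperature is not in the listed review package.

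The SAP (sections 1 and 2.1) records that the trial stopped after two patients. The missing readings cannot now be collected as planned data. That limits what can be done but does not make the schedule sound.

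**What to change.** 1. Add body temperature at visits 3, 4 and 5 (days 3, 7 and 10) in Table 2, section 7.2 and section 8.2.4, taken with the vital signs already scheduled. Reword the visit 3 to 6 sentence in 7.2 so that temperature is no longer restricted to visit 6.
2. If temperature is meant to inform the day-14 dose-escalation review, add it to the review data listed in 5.1 and 5.3. The schedule change alone does not do this.
3. For the trial as it ended, state in the clinical study report that no temperature was scheduled between 24 hours and day 14. The listings in SAP section 4.2 do not name body temperature separately, so say where the recorded values, including any unscheduled ones, are shown.

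Cost of the schedule change: about one minute and one CRF field at each of three existing visits, plus the amendment text. It needs no new visit and changes no treatment or clinical rule. The report statement costs a sentence.

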7.3 Study Flow Chart

Table 2. Study flow chart

Visit number	1	2	3	4	5	6	7	8
	Screening	Treatment period						EOS
Assessment/Day	-28 to -4	0-1	3	7	10	14	30	64
Informed Consent	x							
Demographics	x							
Medical history	x	x ^b						
Inclusion/exclusion	x	x ^b						
Physical examination	x						x	x
Weight	x	x ^b				x	x	x
Height	x							
Vital signs (blood pressure & pulse respiratory frequency)	x	x ^a	x	x	x	x	x	x
Body temperature	x	x ^c				x	x	x
Clinical chemistry (incl. immunoglobulins and ██████████), haematology ██████████, ██████████ urinalysis	x	x ^c	x	x	x	x	x	x
Serum pregnancy test	x	x ^b						x
ADAMTS13 activity	x	x ^c	x	x	x	x	x	x
ADAMTS13 antibodies	x	x ^c	x	x	x	x	x	x
Adverse events	x	x	x	x	x	x	x	x
12-lead ECG	x	x ^a				x	x	x
IdeS infusion		x						
Hydrocortison, paracetamol, antihistamine		x ^b						
Prophylactic antibiotic		x						
IdeS concentration (PK) ██████████		x ^d	x	x	x	x		
██████████		x ^c	x	x	x	x	x	x
PD sampling (IgG SDS-PAGE, IgG and F(ab') ₂ concentration)		x ^c	x	x	x	x	x	x
ImmunoCAP IgG (ADA)		x ^b	x	x		x		x
ImmunoCAP IgE	x							
HIV, Hepatitis B and C	x							
Concomitant medication	x	x	x	x	x	x	x	x

^apredose and 6 h post dose

^bpredose

^cpredose, 2 h, 6 h and 24 h post dose

^dpredose, 45 min (+/- 5 min), 2 h (+/- 15 min), 6 h (+/- 30 min) and 24 h (+/- 2 h) post dose

7.3.1 Recording of Data

The investigator will ensure that all data collected in the study are provided to the Sponsor. He/she ensures the accuracy, completeness, legibility and timeliness of the data recorded in the appropriate sections of the CRF and according to any instructions provided. The principal investigator will provide sponsor with all data produced during the study from the scheduled study assessments. He/she ensures the accuracy, completeness, legibility, and timeliness of the data reported to sponsor in the CRF and in all required reports. The study assessments are described in the sections below and the timing of these assessments are detailed in the study flow chart. Predose assessments should be performed within 60 minutes prior to dosing.

The timing priority order at a particular time point is:

1. Samples for ADAMTS13 activity and ADAMTS13 antibodies
2. █████, █████, Immunoglobulin (safety laboratory parameters)
3. Samples for IgG and F(ab')₂ concentration and samples for IdeS concentration
4. Vital signs
5. ECG

7.3.2 Patient Care After End of Study

All study patients will be followed up regularly according to the follow-up routines for TTP patients. The frequencies of outpatient visits will be adjusted individually to the state of patient health.

8. STUDY ASSESSMENTS

All sampling, shipping and analysing of laboratory samples will be detailed in the laboratory manual. All safety samples as well as [REDACTED], Immunoglobulins and [REDACTED] will be analysed using standard tests by HSL at University College London Hospitals, UK, unless otherwise stated in the respective sections below.

8.1 Assessments Related to Endpoints

8.1.1 ADAMTS13 Activity

Evaluation of the primary endpoint will be analysed using fluorescence resonance energy transfer (FRET) assay for ADAMTS13 activity. The results will be confirmed using a commercial chromogenic Technozym® ADAMTS-13 Activity ELISA. The tests will be performed at HSL at University College London Hospitals, UK. Samples will be drawn at the time points indicated in the study flowchart.

8.1.2 ADAMTS13 Antibodies

Evaluation of the primary endpoint will be analysed using an IgG ELISA. The results will be confirmed using a commercial chromogenic Technozym® ADAMTS-13 autoantibody ELISA. The tests will be performed at HSL at University College London Hospitals, UK. Samples will be drawn at the time points indicated in the study flowchart.

8.1.3 Vital Signs

Blood pressure (systolic and diastolic arterial pressure, including calculation of mean arterial pressure), pulse and respiratory frequency will be measured at time points indicated in the study flowchart.

Systolic and diastolic blood pressure will be measured after the patient has been in supine position for at least 5 minutes. All recordings will be performed using validated standard equipment. Clinically significant abnormal findings will be reported as AEs.

8.1.4 Adverse Events

AEs will be recorded during the trial period, from obtaining the informed consent to the follow-up visit. For further information on definitions and reporting of AEs and SAEs, see Section 8.4.

8.1.5 Clinical Laboratory Variables

8.1.5.1 Clinical Chemistry and Haematology

Blood samples for safety laboratory evaluations of clinical chemistry and haematology parameters (see Table 3) will be collected at the time-points indicated in the study flow chart. Actual sampling time will be recorded. Clinically significant abnormal findings will be reported as AEs. The clinical chemistry and haematology will be analysed locally.

8.1.5.2 Urinalysis

Urine samples (see Table 3) are taken at the time points indicated in the study flowchart. Samples will be analysed locally. In case of abnormal results, a microscopic test will be performed.

Table 3. The following safety laboratory variables will be measured

Clinical chemistry	Coagulation
P-Alanine aminotransferase	P-Activated partial thromboplastin time (APTt)
P-Albumin	P-PK (internationally normalized ratio [INR])
P-Alkaline phosphatase	
P-Aspartate aminotransferase	Haematology
P-Bilirubin, total	B-Haemoglobin
P-Bilirubin, indirect	B- Haematocrit
P-Calcium	B- Reticulocytes
P-Cholesterol	B- Neutrophils, lymphocytes eosinophils, and basophils
P-Creatine phosphokinase	B- White blood cell count with differential count
P-C-reactive protein	
P-Creatinine	B- Red blood cell count
P- Gamma-glutamyltransferase	B- Monocytes, large unclassified cells
P-Glucose	Mean cellular volume
P-Potassium	Mean corpuscular haemoglobin content
P-Sodium	Mean corpuscular haemoglobin concentration
P-Magnesium	
P-Phosphorus	Urinalysis
P-haptoglobin	U-Glucose
P-triglycerides	U-Haemoglobin
P- troponin T	U-Protein
P-Urea (blood urea nitrogen)	U-bilirubin
P-IgG	U-pH
P-Total protein	U-Nitrite
P-Lactate dehydrogenase	U-Ketone
P-immunoglobulins (IgG, IgM and IgGA)	U-Urobilinogen

